#### Per Protocol

- Pre dilatation per the investigators' discretion
- Post dilation is required for each implanted stent
- No more than 3 target lesions in 2 epicardial vessels
- Two target lesions in one epicardial vessel may be stented if at least 15mm apart or can be covered with one stent
- Post dilatation is required for all stents implanted followed by IVUS (for each stent). Up to 2 post dilations and IVUS can be done for each implanted stent
- If two target lesions are treated, post-procedure IVUS imaging must be done on the first target lesion after its successful treatment, and then after successful treatment of the 2nd target lesion

#### IVUS Guide (see Amendment 1)

- All target lesions must have IVUS post dilatation followed by IVUS
- If the stent is not fully opposed the stent must be re-dilated and IVUS repeated after each dilatation
- If the cross sectional area of the stent is less than the distal vessel diameter after the 2nd post dilatation and repeat IVUS, the patient is excluded

#### Bailout Stenting

IF a bailout stent is required it is recommended to use a SYNERGY™ Stent. IVUS must be done per the IVUS protocol for any bailout stents used.

**Post Procedure (Prior to Discharge)**

- Post procedure labs: BMP, CBC with diff and platelets, cardiac enzymes (CPK, CK-MB or Troponin I) 2 sets 6-8 hours apart
- Note: if patient is being discharged the same day draw one set of cardiac enzymes immediately post procedure and one set at 6 hours post procedure.
- 12 Lead ECG

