## 1.2 STUDY DESIGN

## 1.3 SCHEDULE OF ACTIVITIES (SOA)

Procedures	Screening/ Baseline a	Index Procedure (Day 1)	Post-Index Procedure b (Prior to discharge)	30 Days (+ 7 days) Post PCI ) (in office)	60 days (+7 days) Post PCI (In office or via phone)	7 months (+14 days i ) Post PCI (In office or via phone)	13 Months (+ 30 days j ) Post PCI (In office or via phone)
Informed Consent	X						
H&P c	X						
CBC w Diff, platelets	X		X				
BMP	X		X				
PT/INR (only if on warfarin, liver disease or severe anemia)	X		X				
CPK, CK-MB or Troponin-I	X		X d				
EKG	X		X				
ConMeds (Only Cardiac)	X		X	X	X	X	X
Cardiac Cath w PCI		X					
ASA LD	X e						
ASA MD		X f		X		X	X
P2Y12 LD		X g					
P2Y12 MD			X h	X		X	X
AE assessment		X	X	X	X	X	X
Angina assessment k				X	X	X	X
Angina Questionnaire				X			
EDC Completion	X	X	X	X	X	X	X

- a to be completed  $\leq$  7 days prior to Index procedure
- b To be completed within 24 hours after Index procedure
- c Determination of high risk of bleeding (HRB)
- d Perform 2, 6-8 hours apart, if cardiac enzyme levels are elevated (i.e. exceed the upper limits of normal as defined by local guidelines), serial measurements be performed until a decline is noted. If same day discharge draw one set immediately post PCI then 2nd set @ 6-8 hours after
- e Aspirin loading dose (LD) = 325 mg. Start day of procedure (if not on chronic ASA)
- f Aspirin maintenance dose (MD) = 81 mg. Start the day after aspirin loading dose
- g P2Y12 Inhibitor Loading Dose (investigator preference): clopidogrel 600 mg PO x 1 or 75 mg PO daily x 4; prasugrel 60 mg PO x 1; ticagrelor 180 mg PO x 1. Start within 7 days of procedure.
- h P2Y12 Inhibitor Maintenance Dose (investigator preference): clopidogrel 75 mg PO daily; prasugrel 10 mg PO daily; ticagrelor 90 mg PO BID. Start day after P2Y12 inhibitor loading dose
- i 6 months post DAPT cessation
- j 12 months post DAPT cessation
- k Angina Assessment only at 60 days, 7 months and 13 months

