## 4 STUDY DESIGN

### 4.1 OVERALL DESIGN

SYNIVUS-DAPT is a prospective multicenter single-arm pilot study designed to characterize the safety of 1 month of dual antiplatelet therapy (DAPT) in a high bleeding risk (HBR) patient population who are undergoing iLab™ IVUS-guided percutaneous coronary intervention (PCI) with a SYNERGY™ Stent System.

Hypothesis – one (1) to thirteen (13) month rates of cardiac death or myocardial infarction (SCAI definition), and Stent thrombosis after Boston Scientific IVUS-guided SYNERGY™ Stents implantation will be low and provide key hypothesis-generating information to inform future larger scale clinical studies.

Patients will be screened as per standard of care (please see Section 1.3 Schedule of Activities). Eligible patients will undergo iLab™ IVUS-guided PCI with SYNERGY™ Stent System on Day 1 followed by safety laboratories (CBC w Diff, Platelets, Basic Metabolic Panel, PT/INR, CPK/CK-MB or troponin) and EKG within 24 hours of procedure completion. At 30 days ( $\pm$  7 days) patient will return to clinic for evaluation, followed by phone follow up at 30 days post DAPT cessation (60 days post PCI) 6 months ( $\pm$  14 Days) and at 12 months ( $\pm$  30 days) post-DAPT cessation (7 and 13 months post-procedure) for evaluation of adverse events and endpoints.

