#### **General Exclusion criteria:**

1. Subject with an indication for the index procedure of acute ST elevation MI (STEMI)
2. Subject with an indication for the index procedure of Non ST elevation MI (NSTEMI), based on the 3rd Universal MI definition
3. Subject with treatment with another coronary stent, other than SYNERGY, during the index procedure
4. Subject with a planned staged procedure  $> 7$  days following the index procedure. (Note: Planned staged procedures are allowed if performed within 7 days of the index procedure and only when

- SYNERGY™ stents are used for both the index and staged procedures). Discontinuation of DAPT should occur 1 month after the last PCI procedure is completed
5. A staged procedure cannot be in a 3rd epicardial vessel if 2 epicardial vessels were treated during the index procedure
  6. Subject has a known allergy to:
    - a. Contrast (that cannot be adequately pre-medicated),
    - b. SYNERGY™ Stent system (e.g., everolimus, structurally related compounds, polymer or individual components) or
    - c. Protocol-required concomitant medications ( all P2Y12 inhibitors and aspirin)
  7. Subject previously treated at any time with intravascular brachytherapy
  8. Subject has an active peptic ulcer or active gastrointestinal (GI) bleeding
  9. Subject is participating in an investigational drug or device clinical trial that has not reached its primary endpoint (Note: registry, observational, data collection studies are not exclusionary)
  10. Subject intends to participate in an investigational drug or device clinical trial within 12 months following the index procedure (Note: registry, observational, data collection studies are not exclusionary)
  11. Subject is judged inappropriate for discontinuation from P2Y12 inhibitor use at 1 month, due to another condition requiring chronic P2Y12 inhibitor use
    - a. If at the 30 day visit the patient has had a peri-procedural NSTEMI with an enzyme elevation >5% of the upper 99th percentile of either CK-MB or Troponin, the subject should not be taken off DAPT.
  12. Subject with planned surgery or procedure necessitating discontinuation of P2Y12 inhibitor within (≤)1 month following index procedure
  13. Subject is a woman who is pregnant or nursing
  14. Subject with a current medical condition with a life expectancy of less than 12 months
  15. Subject with implantation of a drug-eluting stent other than SYNERGY™ Stents within 11 months prior to index procedure

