#### Pre Procedure Tests and Procedures (Up to 7 days prior to the procedure)

- Standard Laboratory Values: Basic Metabolic Panel, CBC w/ differential and platelets
- Cardiac Enzymes: Total CPK/CK-MB or Troponin I

- PT-INR: If not part of standard of care draw only if patient is taking warfarin, has liver disease or severe anemia
- 12 Lead ECG

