### 7 STUDY INTERVENTION DISCONTINUATION AND PARTICIPANT DISCONTINUATION/WITHDRAWAL

#### 7.1 DISCONTINUATION OF STUDY PARTICIPATION

Subjects should not discontinue P2Y12 inhibitor (the patient will remain in the study until 13 months unless consent to participate is withdrawn) at 1 month if any of the following criteria are met:

- Subject experiences a stroke, MI, PCI, CABG and/or stent thrombosis, during the 1 month period following the index procedure
- Subject is non-compliant with DAPT regimen during the 1 month period following the index procedure. Non-compliant is defined as: DAPT interruption for at least 3 days.
- Subject judged to have another condition rendering them inappropriate for discontinuation from P2Y12 inhibitor at 1 month.

An investigator may discontinue or withdraw a participant from the study if:

- Pregnancy occurs
- Significant study non-compliance beyond DAPT compliance issues

- Continued participation in the study would not be in the best interest of the participant due to other conditions
- The participant is unwilling or unable to discontinue DAPT within 7 days after 30-day post-procedure visit
- Other unforeseen reason

Additionally, participants may withdraw from participation in the study at any time upon their own discretion and a request to the site.

The reason for participant discontinuation or withdrawal from the study will be recorded on Case Report Form (CRF). Subjects who sign the informed consent form but screen fail due to inclusion or exclusion criteria requirements will be replaced.

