**MYOCARDIAL INFARCTION –SCAI Definition – Procedural Related MI****Group                      Definition**

**Normal baseline CK-** CK-MB rise of  $\geq 10$  ULN or  $\geq 5$  ULN with new pathologic Q-waves in at least 2 contiguous leads or new persistent left bundle branch block  
**MB**  
OR  
In the absence of baseline CK-MB, a cTn rise of  $\geq 70$  ULN or a rise of  $\geq 35$  ULN plus new pathologic Q-waves in at least 2 contiguous leads or new persistent left bundle branch block

**Elevated baseline** A CK-MB or cTn rise that is equal (by an absolute increment) to the **biomarkers that are** definitions described for patients with normal CK-MB at baseline. **stable or falling**

**Elevated baseline** A CK-MB or cTn rise that is equal (by an absolute increment) to the **biomarkers that** definitions described for patients with normal CK-MB at baseline  
**have not been** *Plus*  
**shown to be stable** New ST-segment elevation or depression  
**or falling** *Plus*  
New-onset or worsening heart failure or sustained hypotension or other signs of a clinically relevant MI.

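### The enzyme schedule accepts total CPK alone and does not require matching markers before and after PCI, so procedural MI, and with it membership of the primary set, may not be assessable in some patients

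*Combined protocol and SAP*

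**What the plan says.** **Collection.** Four places state which enzymes are drawn.

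- Section 1.3, Schedule of Activities, one row for baseline and post-procedure: "CPK, CK-MB or Troponin-I". Footnote d covers timing and serial draws only.
- Section 6.1.1, post-procedure: "cardiac enzymes (CPK, CK-MB or Troponin I) 2 sets 6-8 hours apart".
- Section 6.1.1, pre-procedure: "Cardiac Enzymes: Total CPK/CK-MB or Troponin I".
- Section 4.1, post-procedure laboratories: "CPK/CK-MB or troponin".

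**Use.** Three rules depend on the result.

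- Section 8.1.1, procedural MI (SCAI): with a normal baseline, a CK-MB rise of at least 10 times ULN, or at least 5 times with new Q-waves or persistent LBBB. The troponin alternative begins "In the absence of baseline CK-MB, a cTn rise of" at least 70 times ULN, or at least 35 times with the same ECG changes. The elevated-baseline groups need "A CK-MB or cTn rise that is equal (by an absolute increment) to the" normal-baseline thresholds.
- Section 5.2 and the Synopsis, exclusion 11a: a peri-procedural NSTEMI with "enzyme elevation >5% of the upper 99th percentile of either CK-MB or Troponin" means the patient stays on DAPT.
- Section 7.1: the P2Y12 inhibitor is not stopped at one month if "Subject experiences a stroke, MI, PCI, CABG and/or stent thrombosis, during the 1 month period following the index procedure".

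Sections 1.1 and 3 define the primary (as-treated) population as the patients eligible for DAPT cessation at 30 days.

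**The concern.** The data a site must collect and the data the MI rule needs are not the same. A site can follow the schedule exactly and still not hold a value to which the procedural MI thresholds apply.

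MI status in the first month is one of the criteria that decide eligibility for cessation, and eligibility defines the primary set. If no usable marker was run, the likely result is that no MI is recorded and the patient is treated as eligible. Section 9.4.2 excludes missing data, but this gap would not show up as a missing endpoint value. The committee that also serves as clinical events committee (Section 10.3) cannot apply a CK-MB or troponin threshold to an assay that was never run.

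**Working it through.** The plan gives no figure on this point, so the check sets the permitted marker pairs against the two rules. With three markers allowed before PCI and three after, there are 3 × 3 = 9 pairs. The comma lists are taken as alternatives and the MI definition is applied as written.

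| Before PCI | After PCI | Procedural MI (8.1.1) | 11a enzyme threshold |
|---|---|---|---|
| any of the three | CPK | not assessable | not readable |
| CPK | CK-MB | no baseline CK-MB to measure a rise from; no post-PCI troponin | readable |
| CPK | troponin | troponin branch opens, but no baseline troponin to measure a rise from | readable |
| CK-MB | troponin | no post-PCI CK-MB; troponin branch closed by the baseline CK-MB | readable |
| troponin | CK-MB | troponin branch has no post-PCI troponin; baseline CK-MB unknown | readable |
| CK-MB | CK-MB | assessable | readable |
| troponin | troponin | assessable | readable |

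The first row stands for three pairs. So 3 pairs fail both rules, 4 leave the MI definition unanswered as written while the 11a threshold can be read, and 2 satisfy both (3 + 4 + 2 = 9). In the group of 4, an assessor might presume that an unmeasured baseline was normal. Those patients therefore may not be assessable, rather than certainly are not.

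**Size (assumptions only).** The documents give no share of patients with CPK alone or mismatched markers.

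- If the share were 5% to 10% of the planned 231: 0.05 × 231 = 11.6 and 0.10 × 231 = 23.1, or about 12 to 23 patients. In the initial phase of 100 it would be 5 to 10.
- A wrong placement also needs an actual procedural MI. If 2% to 5% of those patients had one: 0.02 × 11.6 = 0.2 and 0.05 × 23.1 = 1.2, or about 0.2 to 1.2 patients of 231.
- If every site already runs troponin at all draws, both numbers are zero.

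**The case against.** **The CPK-only route is one reading.** The slash in Section 4.1 and in the pre-procedure list can mean a CPK plus CK-MB panel, or troponin. The post-procedure text asks for sets of enzymes, which fits a panel. Total CPK also has a separate use: the definite stent thrombosis criteria in Section 8.1.1 refer to CK above twice ULN. This stands in part. A reader might infer that the plan meant CPK as a stand-alone MI marker, and the documents do not show that. But the comma lists in Section 1.3 and the post-procedure text do permit it, and the four places do not agree.

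**Mismatched markers do not remove every safeguard.** A reader might infer that a mismatch leaves eligibility for cessation wholly undeterminable. It does not. The 11a enzyme threshold needs only a post-PCI CK-MB or troponin and is far lower than the SCAI thresholds, so a large rise would be visible. Section 7.1 also lets the investigator judge a patient inappropriate for cessation on other grounds. This stands, with one limit: 11a also requires that the event be called a peri-procedural NSTEMI, so it does not fully replace the MI definition.

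**The primary event count is not directly affected.** A reader might infer that missed procedural MIs lower the primary event rate. An index procedural MI falls before the 1 to 13 month window and is never a primary event. Only membership of the set is at issue.

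**Other safeguards exist.** A post-procedure ECG is required, events are adjudicated, and supporting documents can be requested for serious events. These help, but they do not supply a missing assay.

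The restriction to CK-MB or troponin also applies only to procedural MI. The spontaneous MI definition accepts cardiac biomarkers generally, with troponin preferred.

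**Conclusion.** The point holds in a limited form. As written, the schedule can be met with total CPK alone, and such a patient cannot be assessed under the procedural MI definition or exclusion 11a. Mismatched markers may defeat the MI definition but leave the 11a enzyme threshold readable. The consequence is possible wrong placement in the primary set, because eligibility for cessation turns partly on a first-month MI.

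This rests on reading the comma lists as alternatives and on applying the MI definition literally. The number of patients is unknown. On the assumed shares it is at most a few tens with an unsuitable marker, and about one or fewer actually misplaced. The case for acting is that the change is cheap and that a marker not run cannot be judged afterwards. A large expected bias is not part of that case.

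**What to change.** Use one wording in all four places (Section 1.3, Section 4.1, and the pre- and post-procedure lists in Section 6.1.1): CK-MB or troponin, the same marker at baseline and at both post-PCI draws; total CPK may be added but does not replace it.

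It would also help to state in Section 9.3 how the analysis handles a patient whose procedural MI status cannot be assessed. That would be an analysis rule only and would leave the clinical criteria for cessation as they are.

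The cost is a wording change. The blood samples are already drawn. A site that runs only total CPK would have to run a different assay on the same sample.

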**Post PCI Follow up Visits**

Follow up visits will occur at 30 and 60 days post PCI, and 7 and 13 months post PCI

**1. 30 Day Post PCI Visit (+ 7 days) in person Visit:****Requirements:**

- Angina Assessment including completion of the angina assessment questionnaire
  - Evaluate for cardiac events: recurring angina, unstable angina, revascularization (TLR or other) or another condition in the opinion of the investigator would prevent stopping DAPT
- Assessment of adherence to DAPT: Interruptions, missed doses, changes in DAPT Medication
- Adverse event assessment and reporting
- Cardiac con medications (including Aspirin)
- DAPT cessation

**2. 60 Day, 7 Month and 13 Month Post PCI Visits**

- Angina Assessment
- Assessment of adherence to Aspirin: Interruptions, missed doses, changes in DAPT Medication
- Adverse Event assessment including evaluation for cardiac events: Recurring angina, unstable angina, revascularization (TLR or other) or other conditions
- Cardiac con medications (including Aspirin and any reintroduction of P2Y12)

---

**6.1.2 DOSING AND ADMINISTRATION*****Antiplatelet Medications***

DAPT Regimen (aspirin + P2Y12 inhibitor) will be reported in the electronic case report form (eCRF) to include the period of time 72 hours prior to the index procedure through the end of the study. Pertinent information regarding the use of antiplatelet medications including dose changes, medication interruptions (greater than 3 days), and medication cessation, must be documented. Post-PCI dosing should be administered in accordance with the individual agents' directions for use (e.g., consistent with warning, precautions, and dose adjustments if needed)

At the discretion of the Investigator patients on warfarin or NOAC may be discharged on the anticoagulant and a P2Y12 without Aspirin. Additionally at the time of the 30 day visit, if the patient continues on the anticoagulant, the P2Y12 may be stopped and low dose Aspirin (81 mg) may be started.

### **P2Y12 Inhibitor Loading and Discharge Dosing**

- For subjects who have been taking a P2Y12 inhibitor for  $\geq$  72 hours prior to the time of the index procedure, a loading dose will not be required.
- For subjects who have not been taking a P2Y12 inhibitor for  $\leq$  72 hours at the time of the index procedure, a loading dose will be recommended to be administered prior to the index procedure or not more than 2 hours after the index procedure. The following doses are recommended:

Clopidogrel: A peri-procedural loading dose of 600 mg PO x 1 or 75 mg PO daily for 4 days is recommended. A post-procedural daily dose of 75mg will be recommended.

Prasugrel: A peri-procedural loading dose of 60 mg is recommended. A post procedural daily dose of 10 mg will be recommended.

Ticagrelor: A peri-procedural loading dose of 180 mg is recommended. A post procedural dose of 90mg BID will be recommended

### **Aspirin Loading Dose**

- For subjects who have been taking Aspirin daily (regardless of the dose) for  $\geq$  72 hours prior to the time of the index procedure, a loading dose will not be required.
- For subjects who have not been taking Aspirin daily for  $\geq$  72 hours at the time of the index procedure, a loading dose of Aspirin (325mg) is recommended prior to the index procedure. The dosage of the loading dose is at the discretion of the Investigator with a recommendation that it is administered prior to the index procedure.
- A post procedural dose of Aspirin 81mg is recommended.

## **6.2 PREPARATION/HANDLING/STORAGE/ACCOUNTABILITY**

### **6.2.1 ACQUISITION AND ACCOUNTABILITY**

Study participants will undergo SYNERGY™ Stent implantation and receive prescriptions for aspirin and the investigator's choice of P2Y12 inhibitor. Antiplatelet agents and SYNERGY™ Stent are commercially available and will not be provided as part of this study.

## **6.3 MEASURES TO MINIMIZE BIAS: RANDOMIZATION AND BLINDING**

Not applicable. This is not a randomized study.

#### 6.4 STUDY INTERVENTION COMPLIANCE

Compliance to DAPT regimen will be ascertained at the 1-month follow-up visit and will be used to determine if the subject is eligible for discontinuation of P2Y12 inhibitor. During the 1-month follow-up visit, the subject will also be asked about any significant interruptions (greater than 3 days) in the prescribed index procedure.

Follow up at 30 days post DAPT cessation either by phone or clinic visit to assess angina status and targeted endpoints.

Note: All enrolled subjects who receive a SYNERGY™ Stents must be followed at all milestones through 13-months, regardless of eligibility to discontinue DAPT.

##### 6.4.1 RESCUE MEDICINE

Not applicable.

### 7 STUDY INTERVENTION DISCONTINUATION AND PARTICIPANT DISCONTINUATION/WITHDRAWAL

#### 7.1 DISCONTINUATION OF STUDY PARTICIPATION

Subjects should not discontinue P2Y12 inhibitor (the patient will remain in the study until 13 months unless consent to participate is withdrawn) at 1 month if any of the following criteria are met:

- Subject experiences a stroke, MI, PCI, CABG and/or stent thrombosis, during the 1 month period following the index procedure
- Subject is non-compliant with DAPT regimen during the 1 month period following the index procedure. Non-compliant is defined as: DAPT interruption for at least 3 days.
- Subject judged to have another condition rendering them inappropriate for discontinuation from P2Y12 inhibitor at 1 month.

An investigator may discontinue or withdraw a participant from the study if:

- Pregnancy occurs
- Significant study non-compliance beyond DAPT compliance issues

- Continued participation in the study would not be in the best interest of the participant due to other conditions
- The participant is unwilling or unable to discontinue DAPT within 7 days after 30-day post-procedure visit
- Other unforeseen reason

Additionally, participants may withdraw from participation in the study at any time upon their own discretion and a request to the site.

The reason for participant discontinuation or withdrawal from the study will be recorded on Case Report Form (CRF). Subjects who sign the informed consent form but screen fail due to inclusion or exclusion criteria requirements will be replaced.

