#### **Prasugrel (Effient®)**

Prasugrel can cause significant, sometimes fatal, bleeding.

Do not use prasugrel in patients with active pathological bleeding or a history of transient ischemic attack or stroke.

In patients who are  $\geq$  75 years of age, prasugrel is generally not recommended because of the increased risk of fatal and intracranial bleeding and uncertain benefit, except in high-risk patients (diabetes or prior MI), where its effect appears to be greater and its use may be considered.

Do not start prasugrel in patients likely to undergo urgent coronary artery bypass graft surgery (CABG).

When possible, discontinue prasugrel at least 7 days prior to any surgery.

Additional risk factors for bleeding include:

- Body weight  $<$  60 kg
- Propensity to bleed
- Concomitant use of medications that increase the risk of bleeding

Suspect bleeding in any patient who is hypotensive and has recently undergone coronary angiography, percutaneous coronary intervention (PCI), CABG, or other surgical procedures in the setting of prasugrel. If possible, manage bleeding without discontinuing prasugrel. Stopping prasugrel, particularly in the first few weeks after acute coronary syndrome, increases the risk of subsequent cardiovascular events.

For more information on pasugrel please see Effient® package insert.

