#### **Ticagrelor (Brilinta®)**

Ticagrelor, like other anti-platelet agents, can cause significant, sometimes fatal bleeding.

Do not use ticagrelor in patients with active pathological bleeding or a history of intracranial hemorrhage.

Do not start ticagrelor in patients undergoing urgent coronary artery bypass graft surgery (CABG).

If possible, manage bleeding without discontinuing ticagrelor. Stopping ticagrelor increases the risk of subsequent cardiovascular events.

Maintenance doses of aspirin above 100 mg reduce the effectiveness of ticagrelor and should be avoided.

For more information on ticagrelor please see Brilinta® package insert.

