**General Inclusion criteria:**

1. Subject is considered at high risk for bleeding, defined as meeting one or more of the following criteria at the time of enrollment:
  - $\geq$  75 years of age and, in the opinion of the investigator, the risk of bleeding associated with  $>1$  months of DAPT outweighs the benefit,
  - Need for chronic or lifelong anticoagulation therapy

- History of major bleeding (severe/life threatening or moderate bleeding based on the GUSTO classification) within 12 months of the index procedure,
  - History of stroke (ischemic or hemorrhagic),
  - Renal insufficiency (creatinine  $\geq 2.0$  mg/dL) or failure (dialysis dependent),
  - Platelet count  $\geq 20,000/\mu\text{L}$  to  $\leq 100,000/\mu\text{L}$
  - In the opinion of investigator, patient is at significant risk of falling
  - Patient abuses drugs or alcohol
  - Hemoglobin  $\leq 11.0$
2. Subject must be 18 years of age
  3. Subject must be able to take study required dual antiplatelet therapy (1 month of P2Y12 inhibitor and aspirin, 13 months of antiplatelet monotherapy)
  4. Subject is willing to comply with all protocol requirements, including agreement to stop taking P2Y12 inhibitor at the 1-month milestone if eligible per protocol
  5. Subject (or legal guardian) understands the trial requirements and the treatment procedures and provides written informed consent before any trial-specific procedures are performed

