**GUSTO Severe/life-threatening or moderate bleeding**

- Severe or life-threatening: Either intracranial hemorrhage or bleeding that causes hemodynamic compromise and requires intervention
- Moderate: Bleeding that requires blood transfusion but does not result in hemodynamic compromise

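### Section 7.1 lists any month-1 stroke as a reason to keep the P2Y12 inhibitor on, with no exception for hemorrhagic stroke, and does not refer to the protocol's own agent warnings

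*Combined protocol and SAP*

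**What the plan says.** Section 7.1 gives three criteria under which the P2Y12 inhibitor should not be stopped at 1 month while the subject stays in the study. The first is "Subject experiences a stroke, MI, PCI, CABG and/or stent thrombosis, during the 1 month period following the index procedure". The second is non-compliance with DAPT, defined as an interruption of at least 3 days. The third is "Subject judged to have another condition rendering them inappropriate for discontinuation from P2Y12 inhibitor at 1 month".

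Section 8.1.1 defines death, stent thrombosis, bleeding and MI, but not stroke. Where the protocol does specify stroke type, in the high-bleeding-risk criteria of Sections 1.1 and 5.1, it includes both: "History of stroke (ischemic or hemorrhagic".

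The agent-specific risk text in Section 2.3.2 says, for prasugrel, "Do not use prasugrel in patients with active pathological bleeding or a history of transient ischemic attack or stroke". For ticagrelor it says "Do not use ticagrelor in patients with active pathological bleeding or a history of intracranial hemorrhage". For clopidogrel it only points to the package insert.

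Section 6.1.2 asks that dosing after PCI follow each agent's directions for use, including warnings and precautions. It also requires interruptions and cessation of antiplatelet drugs to be documented.

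**The concern.** The three criteria protect subjects for whom early cessation would be unsafe on thrombotic grounds. An ischemic stroke fits that purpose. A hemorrhagic stroke does not obviously fit it, because the concern then is further bleeding. Because the word is unqualified, both types trigger the same advice to keep the drug on.

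The trial enrolls patients because they bleed easily: prior stroke, chronic anticoagulation, low platelets and fall risk all qualify. An intracranial bleed in month 1 is therefore foreseeable, even if uncommon. A site that follows Section 7.1 to the letter has a written reason to continue P2Y12 therapy after such a bleed. A site that stops the drug may wonder whether it has departed from the protocol. A further major bleed after month 1 would count in the secondary GUSTO bleeding endpoint for months 1 to 13.

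**Working it through.** No arithmetic applies. The check sets the Section 7.1 rule beside every other provision that bears on a stroke in month 1.

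1. **Scope of the trigger.** Section 7.1 does not qualify the word and Section 8.1.1 does not define it. The eligibility criteria use it for both types. The literal scope is therefore any stroke.

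2. **Rule against agent warnings.** Section 7.1 names the drug class, not an agent. If the agent is left unchanged:
   - *Prasugrel.* A subject with a month-1 stroke of either type has a history of stroke from that date. Continuing prasugrel conflicts with its warning in Section 2.3.2.
   - *Ticagrelor.* A subject with a hemorrhagic stroke has a history of intracranial hemorrhage. Continuing ticagrelor conflicts with its warning. After an ischemic stroke there is no conflict in the text.
   - *Clopidogrel.* The protocol prints no warning, so there is no conflict in the text. For a hemorrhagic stroke, Section 7.1 still advises continued therapy after an intracranial bleed.

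3. **Effect of changing agent.** A switch to clopidogrel removes the printed conflicts for prasugrel and ticagrelor. It does not remove the advice to keep a P2Y12 inhibitor going after an intracranial bleed. Section 7.1 does not mention a switch.

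4. **The second criterion.** Suppose a site stops the drug because of the bleed and the gap reaches 3 days. The 30-day visit in Section 6.1.1 requires "Assessment of adherence to DAPT: Interruptions, missed doses, changes in DAPT Medication", so the gap will be recorded. It then meets the Section 7.1 definition of non-compliance, which is also a reason not to discontinue. Narrowing only the stroke wording would leave this second route open.

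5. **Judgment clauses.** The third Section 7.1 criterion, and the 30-day check for "another condition in the opinion of the investigator would prevent stopping DAPT", concern reasons to keep the drug on. The best-interest clause later in Section 7.1 concerns leaving the study, not stopping the drug.

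6. **What works the other way.** Section 6.1.2 applies to all dosing after PCI, including at day 30, and brings in each agent's warnings. It is a general dosing statement. Section 7.1 does not cite it, and nothing says which prevails.

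**The case against.** The strongest reply is that the protocol already handles this. Section 6.1.2 makes agent warnings binding on dosing after PCI, and Section 2.3.2 prints those warnings for two of the three agents. It also foresees unplanned cessation. Section 7.1 is advisory in wording and selects who receives the planned 1-month stop; it is not a bleeding-management rule. An intracranial bleed would normally be managed when it happens, before the 30-day visit. Most of this stands. It lowers the rating, but it does not supply the missing exception or cross-reference.

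A reader might infer more than the documents support in four ways:

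- *That nothing at the 30-day decision favors stopping.* Section 6.1.2 does so, through the agent warnings.
- *That the GUSTO definition contradicts Section 7.1.* The severe category, "Either intracranial hemorrhage or bleeding that causes hemodynamic compromise and requires intervention", is an endpoint definition and says nothing about treatment. The prasugrel and ticagrelor text also prefers to manage bleeding without stopping the drug where that can be done, so the protocol does not treat every bleed as a reason to stop.
- *That it is telling that all three Section 7.1 criteria keep the drug on.* The list is headed as reasons not to stop, so every item must point that way.
- *That Section 7.1 orders a drug stopped for a bleed to be restarted.* It does not say so. It only fails to exclude that reading.

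**Conclusion.** The point holds as a minor safety clarification. Taken literally, Section 7.1 points the wrong way after a hemorrhagic stroke. It also conflicts with the printed warning for prasugrel after any stroke and for ticagrelor after intracranial hemorrhage, unless the agent is changed.

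Few subjects are likely to be affected. The number cannot be derived, because the documents give neither a month-1 stroke rate nor the mix of P2Y12 agents. A reader might infer bias in the primary result, but the documents do not support that. A subject with a month-1 stroke is already ineligible for the planned stop, and so already lies outside the as-treated population of the primary endpoint.

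The conclusion rests on two readings: that unqualified stroke includes hemorrhagic stroke, as the eligibility criteria suggest, and that a general dosing statement does not by itself override a specific list that does not cite it.

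**What to change.** Add to Section 7.1, after the three criteria:

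*After any month-1 stroke or intracranial hemorrhage the subject is ineligible for the planned 1-month cessation for analysis. After a hemorrhagic stroke or other intracranial hemorrhage, no criterion in this list requires continued or restarted P2Y12 therapy; clinical judgment and the agent's warnings take precedence. After an ischemic stroke, a subject on prasugrel is switched to an agent not contraindicated for that subject.*

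The override must cover the whole list because of the interruption criterion. The ineligibility sentence prevents a subject whose drug was stopped for a bleed from being counted as having had the planned cessation. Follow-up to 13 months continues under Section 6.4.

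The cost is a short wording amendment, with no new visit, data field or analysis. As-treated membership does not change for subjects with a stroke. For an intracranial hemorrhage that is not classed as a stroke, the sentence makes ineligibility explicit; at present it would depend on the interruption or judgment criterion.
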